Primary Effectiveness Non-Inferiority: The proportion of patients in the Penumbra System with Separator 3D group who experience TICI 2/3 is no more than .15 below the proportion of patients in the Penumbra System group who experience TICI 2/3.

Additional analyses conducted for secondary endpoints and subgroups will be presented, but not utilized in evaluating the study success or Penumbra System product claims.

3 Sample Size

Approximately 230 patients are to be randomized in a 1:1 ratio to the Penumbra System group (115 patients) or the Penumbra System with Separator 3D group (115 patients).

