3.2 Effectiveness Sample Size Evaluation

The sample size calculations assume that 80% of the standard Penumbra System patients experience success (TICl of 2 to 3) and 80% of the Penumbra System with Separator 3D patients experience success. Based on a binomial non-inferiority analysis with a non-inferiority margin of 15%, a study of 103 patients per group will have 85% power with a one-sided alpha of 0.05. The sample size was adjusted to 115 patients per group to account for up to 10% attrition rate.

Assuming that both the 3D arm and the control arm observe a rate of 80% (82/103), the 95% confidence interval for the difference between groups is (-11.0%, 11.0%). The sample size was calculated for a two-group, one-sided test for two proportions using the normal approximation to the binomial using SAS v 9.2 (SAS Institute, Cary, NC). The output of the proc power procedure for a Pearson Chi-square Test for Two Proportions is provided below.

Computed N Total	
Actual Power	N Total
0.852	206

The sample size calculations support enrolling a total of 230 patients (Table 1).

Table 1. Effectiveness Sample Size Parameters

Penumbra System Success Proportion	0.8
Penumbra System with Separator 3D Success Proportion	0.8
Enrollment Ratio (Control: 3D)	1:1
Power	85%
Alpha	0.05
Number of Sides	1

Null Proportion Difference	-0.15
Sample Size	206 (103 per group)
Estimated Attrition	10%
Total Sample Size	230 (115 per group)

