9.4 Effectiveness Subgroup Analysis

To evaluate the impact of baseline conditions on treatment effect, subgroup analyses will be performed for the primary effectiveness variable, TIC1 2-3, the secondary effectiveness variables (good clinical outcome at 30 days, 90-day mRS 0-2, good neurological outcome at 90 days) and the primary and secondary safety variables. The subgroups below will be used for these analyses:

- Age (< 65 , or ≥ 65)
- Baseline NIHSS (< 20 , or ≥ 20)
- Site of occlusion

The subgroup analysis will be conducted using a logistic regression with terms of treatment group and treatment-by-subgroup interaction. The primary statistical inference is the treatment-by-subgroup interaction, which is tested at the significance level of 0.100. These analyses will be performed on the Intent-To-Treat population. When the treatment-by-subgroup interaction is

statistically significant ($p \leq 0.100$) for a specific subgroup, the treatment group differences will be evaluated within each stratum of that subgroup.

10 Safety Analysis

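### The SAP's subgroup model leaves out the subgroup main effect, so its interaction test can report ordinary prognosis as effect modification

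*SAP*

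**What the plan says.** SAP 9.4 sets out the subgroup analyses by age (cut at 65), baseline NIHSS (cut at 20) and site of occlusion. They apply to TICI 2-3, the three secondary effectiveness outcomes, and the primary and secondary safety variables. The model is given in one sentence: "The subgroup analysis will be conducted using a logistic regression with terms of treatment group and treatment-by-subgroup interaction". The next sentence makes that term the main result: "The primary statistical inference is the treatment-by-subgroup interaction, which is tested at the significance level of 0.100". On the population, the SAP says: "These analyses will be performed on the Intent-To-Treat population". If the test is significant for a factor, "the treatment group differences will be evaluated within each stratum of that subgroup".

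Protocol 9.3.3 lists the same three factors but gives no model. Protocol 9.2 leaves the analysis details to the SAP. SAP 2 says that subgroup results will be shown but will not decide study success or product claims.

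**The concern.** An interaction test asks whether the treatment effect differs between subgroup levels. It answers that question only if the model first allows the outcome itself to differ between levels. The model in SAP 9.4 does not list a term for that.

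Age and baseline NIHSS would be expected to predict mRS, NIHSS improvement and death. With the subgroup term missing, that prognostic difference has to go somewhere, and under common codings it goes into the interaction term. The p ≤ 0.100 rule could then be met because older or more severely affected patients do worse in both arms, and the report would describe a treatment effect that varies with age or severity when none does.

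The section runs three factors over seven variables (TICI 2-3, three clinical outcomes, device- or procedure-related SAEs, mortality and symptomatic ICH), which is 3 × 7 = 21 interaction tests. The safety variables are among those exposed.

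**Working it through.** **Inputs.** Terms, level and population come from SAP 9.4. The number per arm comes from SAP 3: "Approximately 230 patients are to be randomized in a 1:1 ratio", so 115 per arm. The documents give no outcome rates by age or NIHSS, so the subgroup rates below are assumptions shown over a range. Subgroups are taken as binary and equal in size unless stated.

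**The plan's own figures.** The only operating figure for the subgroup test is its 0.100 level. The sample size reproduces. With 80% in each arm and 103 per arm, SE = √(2 × 0.8 × 0.2 / 103) = 0.0557, and power = Φ(0.15/0.0557 − 1.645) = Φ(1.046) = 0.852. Allowing for attrition, 103/0.90 = 114.4, which rounds up to 115.

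**What the model as written estimates.** Let t = 1 for the 3D arm and s = 1 for one subgroup level.

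- *0/1 coding:* logit p = a + b·t + c·t·s. In the control arm logit p = a for both levels. In the 3D arm it is a + b for s = 0 and a + b + c for s = 1. So c is the subgroup log odds ratio within the 3D arm, which is prognosis.
- *Class (nested) coding:* the term has one subgroup contrast in each arm, so the test has 2 df and asks whether the subgroup is prognostic in either arm.
- *−1/+1 coding:* with 1:1 allocation the product column is balanced against the omitted subgroup column. With no treatment effect, prognosis largely cancels.
- *Main effect included:* logit p = a + b·t + d·s + c·t·s. Here c is the difference between arms in the subgroup log odds ratio, which is the interaction.

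**Hand check, outcome 50% v 30%, no treatment effect, no interaction.** Each subgroup level of the 3D arm has 115/2 = 57.5 patients.

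- c = ln(0.5/0.5) − ln(0.3/0.7) = 0.847
- SE = √[1/(57.5 × 0.25) + 1/(57.5 × 0.21)] = 0.390
- z = 0.847/0.390 = 2.17
- Rejection rate with 0/1 coding = Φ(2.17 − 1.645) = 0.70
- With class coding the noncentrality is 2 × 2.17² = 9.4 on 2 df. Against the critical value 4.605 the rejection rate is 0.87.

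**Simulation.** 20,000 trials per row, 115 per arm, no treatment effect, no interaction, likelihood-ratio tests at 0.100. The −1/+1 column uses 4,000 trials and a Wald test.

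| Outcome by subgroup (assumed) | 0/1 coding | Class coding, 2 df | −1/+1 coding | Main effect added |
|---|---|---|---|---|
| 40% v 40% (no prognosis) | 0.105 | 0.103 | 0.100 | 0.098 |
| 45% v 35% | 0.296 | 0.383 | 0.101 | 0.106 |
| 50% v 30% | 0.713 | 0.879 | 0.090 | 0.103 |
| 55% v 25% | 0.957 | 0.997 | 0.084 | 0.105 |
| 85% v 75% | 0.389 | 0.511 | 0.100 | 0.106 |
| 90% v 70% | 0.869 | 0.975 | 0.092 | 0.112 |

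The 50% v 30% row agrees with the hand check.

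**Variations on 50% v 30%** (0/1 coding, class coding, main effect added):

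- 103 per arm: 0.67, 0.84, 0.106
- 35% of patients in the lower-rate subgroup: 0.67, 0.85, 0.101
- Common treatment odds ratio of 1.5, still no interaction: 0.73, 0.89, 0.10

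**The case against.** **It may be shorthand.** The section's stated aim concerns treatment effect, and many readers would take the lower-order term as implied. That is possible. But the sentence lists the model's terms, nothing else in either document adds the missing one, and an analyst who follows the text literally fits the wrong model.

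**The result depends on coding.** This stands. With −1/+1 coding, 1:1 allocation and no treatment effect, the test stays at 7% to 10%. The documents name SAS but no procedure or coding for this model, so the behaviour of a pre-specified test rests on an unstated choice. With the main effect included, the coding no longer matters.

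**The follow-on comparisons are not biased.** This also stands. Within a stratum the comparison is between randomised arms, so prognosis does not distort it. In 6,000 simulated trials with no treatment effect at 50% v 25%, the chance that the interaction test was significant and either stratum then showed an unadjusted Fisher p < 0.05 was 5.8% (0/1) or 7.9% (class). Testing both strata without any gate gives 7% to 8%. The Bonferroni rules in SAP 9.3 and 10.4 could reduce this further. The harm is therefore a misleading interaction p-value and a gate that no longer screens, and not a large number of false stratum-level treatment effects.

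**No decision rests on it.** SAP 2 keeps subgroup results out of study success and product claims. This limits the importance of the point but does not make the test correct.

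**The rates are assumed.** True for age and NIHSS. For occlusion site, protocol section 1 reports recanalization of 82.6% (ICA) and 83% (MCA) in the earlier single-arm study of the device. At those rates the test would run at about its nominal level (10.5% or 11.1%), so TICI by site is probably little affected. Clinical and safety outcomes by age or NIHSS are the likelier problem.

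**Conclusion.** The concern holds. As written, the SAP 9.4 model omits the subgroup main effect. Under 0/1 or class coding its interaction test then measures prognosis and not effect modification. At 115 per arm and a nominal 10%, the false-positive rate is about 30% to 38% for a 10-point prognostic difference (45% v 35%), 71% to 88% for 20 points (50% v 30%), and 96% or more for 30 points (55% v 25%). With the main effect included it is about 10% throughout.

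These sizes rest on assumed subgroup rates and, except where shown, equal-sized binary subgroups. There is no inflation if the factor is not prognostic, and none under −1/+1 coding in the cases run. The effect is confined to how subgroup results are read, including those for safety. The primary non-inferiority conclusion and the sample size are untouched. The SAP should be corrected, but the error does not threaten the trial's main result.

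**What to change.** Amend SAP 9.4 so that each subgroup model contains treatment, the subgroup factor and their product, and say that the interaction test at 0.100 is taken from that model. For occlusion site, list the levels, so that the degrees of freedom of the test are fixed in advance.

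The cost is a phrase in the SAP, and SAP 14 already provides for a revised version. No change to data collection, sample size or the primary analysis is needed. If the main effect was always intended, the amendment only records that.

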10.1 Primary Safety Analysis

The primary safety endpoint is the proportion of patients with a device or procedure related SAE within 24 hours post-procedure. The proportion of patients in each group who meet the safety endpoint based on this criterion will be calculated.

The primary null hypothesis for safety in this study is that there is no difference in device-related and procedure-related serious adverse event rates. This null hypothesis will be tested against the alternative hypothesis that there is a difference between the two treatment groups. The null hypothesis will be rejected at the two-sided significance level of $\alpha = 0.05$. The primary analysis is an analysis of all patients according to treatment received. The Fisher's Exact test will be employed to assess the primary safety endpoint.

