The Penumbra System[®] is a new generation of neuro-embolectomy devices specifically designed to remove thrombus through aspiration.¹⁴⁻¹⁵ The System has received 510(k) clearance from the US FDA for an acute ischemic stroke recanalization indication. The pivotal trial for this clearance was a prospective, single arm, 125 patient study designed to assess the safety and effectiveness of the System to reduce clot burden in acute ischemic stroke, using the Concentric clot retriever (Mountain View, CA) as the predicate device (historical control).¹⁴ The results indicated that the Penumbra System was able to recanalize the site of primary occlusion in over 80% of the patients, which was higher than those reported for the Concentric clot retriever (43% to 54%), or the spontaneous reperfusion rate reported in the untreated control group in the PROACT-II study (18%).^{12,13,19} The high recanalization rate was independent of target vessel locations. Recanalization was successful in 82.6% of patients presenting with occluded target vessels in the ICA, and in 83% of patients presenting with occluded target vessels in the MCA. Among the patients recanalized with the device, 12.8% had procedural complications of which 3.2% were considered serious. None was associated with malfunction or breakage of the device. This procedural event rate is quite favorable when compared to the published rates for other intra-arterial interventions for acute stroke.^{12,13,19,20} These observations are indicative of the ability of the Penumbra System to access the cerebral arteries to safely recanalize the site of primary occlusions in most locations of the brain, and often, in patients with significant tortuosity that would normally hamper intracranial vascular access.

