9.4.1 Primary Safety Analysis

- Analysis of device or procedure related SAE within 24 hours post procedure: The proportion of patients in each group who experience a device or procedure related SAE within 24 post procedure will be calculated. The CEC/DSMB data supersede the investigator-reported data in all analyses Adverse Events. Frequency counts and percentage of patients within each category will be provided. Estimates of the treatment differences and their 95% confidence intervals will be calculated. Subject rates will be compared between treatment groups with Fisher's exact test.

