The deficiency, or a lack of blood flow to an organ resulting in an imbalance between the supply and demand of oxygen (or other nutrients) leading to cell damage or death

LEUKOPENIA

A leukocyte count of $<3.5 \times 10^9$ /liter for more than 3 days

NEOINTIMAL HYPERPLASIA

Thickening of the neointima due to intimal cell accumulation

NEUTROPENIA

A decrease in the number of neutrophilic leukocytes in blood to $<1,000 \text{ mm}^3$

OCCLUSION

The cessation of blood flow in an artery due to the presence of a clot or thrombus

OCCLUSION LOCATION

Location according to specific cerebral artery; a standard code will be provided in the CRF to use for location descriptions

PERFORATION

The piercing or rupturing of a blood vessel; perforations can be detected or observed angiographically

PROCEDURAL SERIOUS ADVERSE EVENTS

Serious adverse events that occurred within 24 hours of the procedure

SERIOUS ADVERSE EVENT

Any undesirable clinical event or serious device effect that results in death, is life-threatening, causes persistent or significant disability/incapacity, requires or prolongs hospitalization, requires intervention, results in congenital abnormality, or led to a serious deterioration in the health of the patient that resulted in life-threatening illness or injury, resulted in permanent impairment of a body structure or a body function, resulted in medical or surgical intervention to arrest permanent impairment to body structure or a body function, or led to fetal distress, fetal death or a congenital abnormality or birth defect

STROKE

A new focal neurological deficit of presumed vascular origin persisting more than 24 hours and with a neuro-imaging study that does not indicate a different etiology. The 24-hour criterion is excluded if the patient undergoes cerebrovascular surgery or dies during the first 24 hours. It includes patients presenting with clinical signs and symptoms suggestive of subarachnoid hemorrhage, intracerebral hemorrhage, or cerebral infarction. It does not include stroke events in cases of blood disorders such as leukemia, and it excludes patients with a history of stroke secondary to trauma.

TARGET OCCLUSION

The occlusion treated or attempted to be treated during the index procedure

TARGET VESSEL

The intracranial vessel containing a target occlusion

THROMBUS

Discrete, mobile intraluminal filling with defined borders with or without associated contrast straining; these are classified as either absent or present.

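### SAP 10.1 rests the primary safety endpoint on a Fisher test with little power to detect harm and omits the risk difference and 95% CI that protocol 9.4.1 requires

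*SAP*

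**What the plan says.** - **Endpoint.** SAP 10.1: "The primary safety endpoint is the proportion of patients with a device or procedure related SAE within 24 hours post-procedure".
- **Test.** The null hypothesis is equal rates in the two arms and the alternative is any difference. "The null hypothesis will be rejected at the two-sided significance level of" 0.05, with patients analysed by treatment received. "The Fisher's Exact test will be employed to assess the primary safety endpoint". The section promises the proportion in each group, but no difference and no interval.
- **Protocol 9.4.1, same endpoint.** "Estimates of the treatment differences and their 95% confidence intervals will be calculated". It names the same test: "Subject rates will be compared between treatment groups with Fisher's exact test".
- **SAP 10.2.** It keeps the difference and 95% interval, but for the secondary safety variables only.
- **SAP 10.4.** Every safety comparison is called secondary and is Bonferroni-adjusted.
- **SAP 2 and 3.2.** Study success depends on effectiveness alone, and the sample size was derived for effectiveness alone.
- **Event rate.** Neither document gives a planning rate for this endpoint. The nearest figure is background on the earlier single-arm pivotal study in the protocol Introduction, where "12.8% had procedural complications of which 3.2% were considered serious".

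**The concern.** A two-sided test of equality, in a trial not sized for safety, will often be non-significant even when the new component does cause more serious events. Fisher's exact test adds to this when events are few, because its attained type I error falls well below the nominal level. On an effectiveness endpoint that caution protects patients; on a safety endpoint it makes an excess of harm harder to detect.

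What a non-significant result leaves open is how large an excess risk is still compatible with the data, and the interval answers that. Protocol 9.4.1 asks for it. The section of the SAP that governs the primary safety endpoint does not, so under the SAP the two secondary safety endpoints are reported more informatively than the primary one.

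**Working it through.** **1. The plan's own figure.** The only sizing is for effectiveness (SAP 3.2): 80% in both arms, margin 0.15, one-sided 0.05, power 85%.

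n per arm = (1.645 + 1.036)² × (2 × 0.8 × 0.2) / 0.15² = 7.19 × 0.32 / 0.0225 = 102.2, rounded up to 103.

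Power at 103: SE = √(0.32/103) = 0.0557; Φ(0.15/0.0557 − 1.645) = 0.852. Attrition: 103/0.9 = 114.4, rounded up to 115. All agree with the SAP. No corresponding figure exists for safety.

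**2. Inputs for the safety check.**
- 115 per arm (SAP 3), assuming every randomized patient is in the safety analysis.
- Two-sided 0.05 and Fisher's exact test (SAP 10.1).
- Event rate: *assumed*, 3.2% to 20%. The low end is the historical 3.2%. Applied to that study's 125 patients, 3.2% is 4 patients and 12.8% is 16, so it reads most naturally as a share of patients. The true rate could be well above it: protocol 11.3 defines procedural serious events as "Serious adverse events that occurred within 24 hours of the procedure", and the Introduction reports symptomatic intracranial haemorrhage in 11.2% with the same system.

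**3. Attained size.** For a common rate π, size = Σ over (a, b) of Bin(a; 115, π) × Bin(b; 115, π), taken over all tables with two-sided Fisher p ≤ 0.05.

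| Common rate | Fisher size |
|---|---|
| 3.2% | 1.5% |
| 5% | 2.1% |
| 8% | 2.5% |
| 12.8% | 3.1% |
| 20% | 3.5% |

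At 103 per arm and 3.2% the size is 1.3%.

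**4. Power.** The same sum with different rates in the two arms. Boschloo's test uses the Fisher p-value as its statistic, with the cut-off raised as far as the maximum size over all common rates allows while staying at or below 5%. The alternatives are illustrative.

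| Rates | Fisher | Boschloo | Mid-p |
|---|---|---|---|
| 3.2% v 6.4% | 12% | 15% | 17% |
| 3.2% v 9.6% | 40% | 45% | 49% |
| 3.2% v 12.8% | 71% | 75% | 78% |
| 10% v 20% | 50% | 54% | 56% |

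Fisher therefore misses a doubling from 3.2% in 88% of trials and a tripling in 60%. At a common rate of 3.2% Boschloo's size is 2.5% and mid-p's is 3.3%. Mid-p's maximum over all common rates is about 5.6%, so it does not guarantee the level, although at the rates tabulated in step 3 it stays below 5%.

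**5. What the interval adds.** Take 12/115 against 4/115 events (10.4% v 3.5%). Fisher gives p = 0.067, not significant. The difference is 8/115 = 7.0 points, with a Miettinen-Nurminen 95% interval of 0.4 to 14.4 points. Under SAP 10.1 alone, a threefold excess would appear as two proportions and a non-significant p-value.

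**6. If the Bonferroni rule in SAP 10.4 applies.** The family size is not stated. Assuming three endpoints (the primary safety endpoint, mortality, symptomatic haemorrhage), each is tested at 0.05/3 = 0.0167. Fisher's size at 3.2% falls to 0.45%, and its power for a tripling to 24%.

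**The case against.** Fisher's exact test is a standard choice, prespecified in both documents. No success decision turns on this p-value. The SAP describes itself as elaborating the protocol's methods, so the protocol's interval still stands, and anyone can compute it from the two reported proportions.

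Much of this stands, and it rules out four stronger readings that a reader might infer:

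- *That the 5% level is misstated.* It is not. A nominal level is an upper bound, and Fisher's test stays within it at every rate. The cost is lost power, not an invalid test.
- *That 1.5% is the size to expect.* The documents give no expected rate. The 3.2% is a historical figure for a related but different quantity, and at rates of 12.8% to 20% the size is 3.1% to 3.5%.
- *That the SAP withdraws the interval.* It is silent in 10.1 and nowhere revokes protocol 9.4.1.
- *That a non-significant result will be reported as equal safety.* Neither document says so. SAP 10.1 states only when the null hypothesis is rejected.

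What the objection does not remove is the gap itself. Protocol 9.2 leaves the full detail of the analyses to the SAP, and SAP 10.2 shows that the interval sentence was thought worth repeating for the secondary safety variables. Silence at the primary safety endpoint leaves its most informative summary to chance.

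**Conclusion.** The point holds as a worthwhile, low-cost improvement, carried mainly by the missing interval. SAP 10.1 does not carry over the difference and 95% CI that protocol 9.4.1 requires. The test it relies on has an attained size of about 1.5% to 3.5% over assumed rates of 3.2% to 20%, and power of 12%, 40% and 71% for a doubling, tripling and quadrupling from 3.2%. The weakness is not confined to very low rates: power is 50% for 10% against 20%.

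Replacing Fisher's test is the smaller part. Boschloo's test gains about 3 to 6 percentage points of power in the scenarios shown; it keeps the maximum size at or below 5% and rejects whenever Fisher's does. Even so, power for a doubling from 3.2% is only 15%, so no choice of test substitutes for the interval.

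Separately, the unadjusted 0.05 in SAP 10.1 and the Bonferroni rule for all safety comparisons in SAP 10.4 cannot both apply.

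These figures assume 115 analysed patients per arm, independent binomial counts, and event rates and alternatives that are not in the documents.

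**What to change.** 1. In SAP 10.1, make the risk difference (Separator 3D minus control) with its 95% score (Miettinen-Nurminen) interval the main safety result. State that a non-significant test is reported through the upper confidence limit, as the largest excess risk still compatible with the data. The interval and an exact test can disagree near the boundary, so say that the interval leads.
2. Replace Fisher's test with Boschloo's exact test in SAP 10.1, with a matching edit to protocol 9.4.1. Mid-p is more powerful, but its maximum size is about 5.6%.
3. State the assumed event rate, or a range, and the resulting power.
4. Reconcile SAP 10.1 with SAP 10.4: say whether the primary safety comparison is adjusted and, if so, over which endpoints.

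Cost: wording edits to the SAP and protocol, and a p-value that may be slightly less favourable to the device. No patients or data are added. Item 1 needs only the SAP edit, because protocol 9.4.1 already requires the difference and a 95% interval.
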